15.3.1 Infections

All infections will be reported as AEs on the AE eCRF. The summaries described in this section will be provided for treatment-emergent infections (defined as for TEAEs). Treatment-emergent infections will be summarized on the basis of information reported on the AE eCRF.

For any infection, the following summaries will be presented by treatment group:

- Number (percent) of patients with at least one infection
- Number and % of infections per patient (0, 1, 2, ...)
- Descriptive statistics for number of infections per patient

The number of infections per patient and per patient-years (cumulative follow-up of each patient) will be provided by year (e.g., 2019, 2020, 2021, etc.) and overall.

A by-patient listing summarizing information on infections will be provided on SAF set.

15.3.2 Malignancies

All malignancies must be confirmed by histopathology. Malignancies are documented as AEs, and will be coded by SOC and PT. The summaries described in this section will be provided for treatment-emergent malignancies (defined as for TEAEs). Malignancies will be identified through a blinded medical review of collected AEs. The result of the medical review will be a flag for the identification of malignancies added in an excel sheet, that will be imported for analysis.

A summary table by SOC and PT and by-patient listing summarizing information collection will be provided on SAF.

L-CsA:

Treatment of BOS after SLT

Protocol Number:

BT – L-CsA – 301 – SLT

Sponsor:

Zambon SpA

15.4 Acute Tolerability of IMP

At Visit 1, acute tolerability of IMP (L-CsA) during initial dosing will be determined by measuring:

- Spirometry (FEV₁, **CCI** [REDACTED], FVC) measured before and **CCI** [REDACTED].
- Spontaneous report of cough or dyspnea, recorded as AE in the appropriate eCRF.

Descriptive statistics of pre-dose (V1), post-dose (**CCI** [REDACTED]) and change from pre-dose will be presented for each spirometry parameter on the SAF population.

In addition, the number and percent of patients experiencing a decline of **CCI** [REDACTED] in FEV₁ will be presented.

The number and percent of patients experiencing new onset or worsening of TEAEs having the following PTs on the date of the first visit at which L-CsA is administered will be summarized:

- Cough;
- Dyspnea.

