#### 12.1.1.4 Onsite visits

On-site spirometry should be performed by blinded personnel.

At every visit, spirometry will be measured using the CCI [REDACTED] and the CCI [REDACTED] spirometers. Instructions for Use (including additional information on accuracy checks, cleaning of the device and further support) for both devices are available in the Study Manual. At least three acceptable and repeatable maneuvers on each device should be obtained at each visit.

At Visit 1, the spirometry at CCI [REDACTED] will only be performed using the CCI [REDACTED]

Sufficient rest between both spirometry sessions should be granted to the subject at the Investigator's discretion. For the CCI [REDACTED] spirometry session, procedures identical to those to be used at home will be followed.

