#### 13.1.1 Adverse Events (AEs)

##### ***13.1.1.1 Definitions***

###### **Adverse Event (AE)**

An AE is any untoward medical occurrence in a patient after administration of a pharmaceutical product and which does not necessarily have a causal relationship with this treatment. An AE can therefore be any unfavorable and unintended sign (including an abnormal laboratory finding), symptom, or disease temporally associated with the use of a medicinal (investigational) product, whether or not related to the medicinal (investigational) product (ICH Guidelines for Good Clinical Practice, E6(R2), 9 November 2016).

This includes worsening of a pre-existing condition or increase in frequency of a pre-existing condition. An adverse event is considered serious if it meets any of the serious criteria listed below. To ensure no confusion or misunderstanding of the difference between the terms “serious” and “severe”, which are not synonymous, the following clarification is provided:

The term “severe” is often used to describe the intensity (severity) of a specific event (as in mild, moderate, or severe myocardial infarction); the event itself, however, may be of relatively minor medical significance (such as severe headache). This is not the same as “serious”, which is based on patient/event outcome or action criteria usually associated with events that pose a threat to a patient’s life or functioning. Seriousness (not severity) serves a guide for defining regulatory reporting obligations.

The official definition also extends to AEs occurring during the off-treatment follow-up period.

Each patient will be closely observed and questioned for AEs throughout the clinical trial period with non-leading questions (e.g., how do you feel?). The patients will be instructed to report to the clinical trial staff immediately any symptoms and/or signs which occur between the scheduled observation times.

All AEs reported by the patient or observed by the Investigator or hospital personnel will be documented in the respective eCRF. The following information regarding each adverse event will be obtained: date and time of onset and resolution (duration), serious or non-serious (as defined below), severity, treatment required, outcome, relationship to certain medication, and if the AE caused withdrawal from the clinical trial.

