#### 14.2.2 Visit 1 / Baseline Visit

##### *Baseline Prior to Start of Treatment*

- Verify Informed Consent was obtained
- Verify Demographics/Medical History
- Verify Inclusion/Exclusion Criteria were met at Screening Visit
- Repeat Serum (or Urine) Pregnancy Test, if result was obtained more than 7 days prior to the visit
- Physical examination
- Vital signs
- Clinical laboratory tests. Not mandatory in case laboratory tests at screening visit have been performed within 2 weeks from Visit 1.
- CCI [REDACTED] (CCI [REDACTED] and CCI [REDACTED] if needed, refresher training for CCI [REDACTED] Patients will be provided with the portable spirometer at the Visit 1 / Baseline Visit only if the patient will be randomized in the study
- Randomization
- Blood sampling for serum levels of calcineurin inhibitors and mTor inhibitors
- Concomitant medications/therapies
- Adverse events
- EQ-5D-5L Questionnaire

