12.2 Other Immunosuppressants

Other immunosuppressants refer to all the immunosuppressive therapies that are not classified as maintenance regimen as described in section 12.1 (but meet the conditions reported in section 12). Other immunosuppressive therapies will be coded by ATC codes, and will be summarized by treatment group for SAF, FAS and PPS.

All other immunosuppressants administered from the day of randomization will be evaluated. The number (%) of patients taking any other immunosuppressants will be provided overall and for each ATC code.

The same summary statistics for cumulative dose and for exposure as described in section 12.1 will be provided.

13 Prior and concomitant medications

Prior medications are those medications taken prior to randomization with a stop date and time prior to the randomization date/time (standard definition of prior/concomitant medications considers the first dose of study treatment but, as in this study SOC group won't have any first dose date, randomization date will be considered instead).

Concomitant medications are those medications with a start date and time on or after the randomization date/time, or those with a start date and time before the randomization date/time and either a stop date and time on or after the study randomization or are ongoing at the end of the study.

Prior and concomitant medications will be summarized by ATC codes and listed for FAS. Prior/concomitant medications will be coded using the WHO-DD classification system and grouped by drug class and PT.

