15.3 Adverse Events

All AEs occurring during the clinical trial, whether or not attributable to study treatment, will be documented in the eCRF. All AEs will be coded to SOCs and PTs using the MedDRA dictionary (version 23.1).

Treatment-emergent adverse events (TEAEs) are defined as AEs with onset on or after the date of randomization.

The Investigator will assess the relationship (unrelated, possible, definite) of each AE to the clinical trial treatment assignment (L-CsA plus SoC or SoC alone). Treatment-related AEs are defined as events the Investigator considers to be possibly or definitely related to clinical trial treatment assignment.

All AEs reported in the eCRF will be presented in by-patient listings for the SAF.

The following summaries will be presented for AEs by treatment group and overall:

- Overview table including the number and percent of patients with
 - AEs;
 - TEAEs;
 - TEAEs leading to discontinuation of study treatment;
 - TEAEs leading study discontinuation;
 - TEAEs leading to death;
 - TEAEs by severity (Mild, Moderate, Severe);
 - Study treatment related TEAEs;
 - Serious TEAEs;
 - Serious study treatment related TEAE;
- TEAEs, grouped within SOC by decreasing frequency of PT;
- TEAEs by decreasing frequency of PT;
- TEAEs leading to discontinuation of study treatment, grouped within SOC by decreasing frequency of PT;
- TEAEs leading to study discontinuation, grouped within SOC by decreasing frequency of PT;
- TEAEs leading to death, grouped within SOC by decreasing frequency of PT;
- TEAEs by maximum severity, grouped within SOC by decreasing frequency of PT;
- TEAEs by relationship, grouped within SOC by decreasing frequency of PT;
- Serious TEAEs, grouped within SOC by decreasing frequency of PT;
- Related serious TEAEs, grouped within SOC by decreasing frequency of PT.

Patients who have multiple events coded to the same PT or within the same SOC will be counted only once in the patient counts for the corresponding summaries, but all events will be considered and listed. Table presentations will contain counts of patients, percentages of patients, and the number of events.

Any AE with missing relationship will be assumed related and summarized in the possible related category to clinical trial treatment assignment. Patients who experience the same event multiple times will be included in the most related category for summarization.

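### The first-dose cough and dyspnea summary in SAP 15.4 selects events by calendar date, so an event that began before the first L-CsA inhalation at Visit 1 would be counted as an acute tolerability event

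*SAP*

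**What the plan says.** SAP 15.4 opens with its purpose: "At Visit 1, acute tolerability of IMP (L-CsA) during initial dosing will be determined by measuring" spirometry before and after the dose, together with cough or dyspnea that patients report spontaneously and that is entered as an adverse event. The symptom summary is then specified as "The number and percent of patients experiencing new onset or worsening of TEAEs". Two conditions narrow it: the preferred term must be cough or dyspnea, and the timing is fixed by the clause "having the following PTs on the date of the first visit at which L-CsA is administered will be summarized".

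SAP 15.3 sets the wider filter. Treatment-emergent events are "defined as AEs with onset on or after the date of randomization". Protocol 15.2.5.2 uses the same date-based rule.

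Protocol 14.2.2 divides Visit 1 into two parts. The first, headed "Baseline Prior to Start of Treatment", includes physical examination, spirometry, randomization and collection of adverse events. The second covers device training and the supervised first inhalation.

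Protocol 13.1.1.1 requires both the date and the time of onset for each adverse event, and the by-patient listings in SAP 15.3 show the start date and time.

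**The concern.** The table is meant to show what followed the first inhalation, but neither of its filters refers to that inhalation. A patient who began coughing during baseline spirometry, had it recorded as an adverse event, and was then randomized and dosed would appear in the same row as a patient who coughed because of the drug.

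The row is tied to L-CsA administration, so it has no standard-of-care count that would show the background level of such events. Misplaced pre-dose events can only raise the L-CsA figure. In a small arm, one or two of them would visibly change the rate.

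**Working it through.** The plan gives no figure for this point, so there is nothing to reproduce. The check is of the text, followed by a scale calculation.

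**Step 1: the selection rule.** An event enters the 15.4 row if (a) it is coded as cough or dyspnea, (b) it is treatment-emergent, and (c) it is new or worsened on the date of the first L-CsA visit. Condition (b) is met by any onset on the randomization date. For a patient dosed at Visit 1, (b) and (c) point to the same calendar day, and neither carries a clock time.

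**Step 2: is there a pre-dose interval on that day?** Yes.
- Protocol 14.2.2 puts examination, spirometry, randomization and adverse event collection ahead of the first dose.
- Footnote 5 of the Schedule of Activities places Visit 1 spirometry before randomization.
- Protocol 12.1.1.3 requires spirometry to precede L-CsA inhalation.
- Protocol 12.1.1.4 adds: "At least three acceptable and repeatable maneuvers on each device should be obtained at each visit".

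**Step 3: does anything else exclude a pre-dose event?** The requirement that the event be new or worsened states no reference time. The missing-date rules in SAP 9.5.3.2 anchor incomplete starts to randomization, which still precedes the inhalation. No other section removes such events.

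**Step 4: could the plan use time instead?** Onset time is collected and listed. Two neighbouring rules already separate before from after: the spirometry half of 15.4 compares pre-dose with post-dose values, and SAP 13 classes medications as concomitant if they are "with a start date and time on or after the randomization date/time".

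**Step 5: scale.** SAP 8.2 gives 62 patients randomized. Arm sizes are not stated, so 62 / 2 = 31 is an assumption from 1:1 allocation.
- One patient whose only qualifying event began before dosing: 1 / 31 = 3.2 percentage points.
- If the dosed arm were instead anywhere from 28 to 34 (an assumed range): 1 / 28 = 3.6 points down to 1 / 34 = 2.9 points.
- The number of such patients is unknown. If it is zero, the effect is zero.

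**The case against.** **The qualifier may already exclude them.** Under a heading about initial dosing, a new or worsened event could be read as relative to the patient's state before the dose. That reading is reasonable, but it is not written down. A programmer following the text has only the date to work with.

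**Adverse events are defined as following a product's administration** (Protocol 13.1.1.1). In practice the plan collects them earlier: Protocol 14.2.1 and 14.2.2 list adverse events at Screening and in the pre-treatment part of Visit 1, and SAP 15.3 tabulates all adverse events separately from treatment-emergent ones.

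**Impact is limited.** This stands. SAP 15.1 plans no inferential safety analysis, and a reader can check Visit 1 events in the listings. A cough during a maneuver also need not become an adverse event. Protocol 12.1.1.1 treats cough in the first second as a test artefact, and 15.4 counts only spontaneous reports entered as adverse events.

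**Stronger readings that the documents do not support.**
- A reader might infer that these patients are classed as intolerant of L-CsA. They are not. Protocol 10.3.1.1 ties intolerance to a fall in FEV1 with respiratory symptoms, and the 15.4 row is descriptive.
- A reader might infer that the treatment-emergent definition in 15.3 is also faulty. It follows Protocol 15.2.5.2, is inclusive in the usual way for safety data, and applies to both arms before assignment is known, so no between-arm bias is expected.
- A reader might infer that every patient performs at least six forced maneuvers before dosing. That holds only where both spirometers are used, and the synopsis introduces the portable device for patients newly enrolled under protocol version 3.0 or later.
- A reader might take two misplaced events (2 / 31 = 6.5%) as an expected error. The documents supply no such count.

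**Conclusion.** The point holds for SAP 15.4 only. As written, a cough or dyspnea event that began on the day of the first L-CsA visit, but before the inhalation, would be counted in a table intended to show tolerability of that inhalation. Each such patient would add about 3.2 percentage points if roughly 31 patients received L-CsA. The number affected is not given and may be zero. The conclusion rests on reading the date rule literally and on first doses being given at Visit 1, as the protocol schedules. It is a cheap improvement to a descriptive safety table and has no bearing on the efficacy analysis or the general adverse event tables.

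**What to change.** Change SAP 15.4 only:

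1. Count cough and dyspnea events whose onset or worsening date and time is at or after the start of the first L-CsA inhalation on that day.
2. Keep same-day events with no recorded time in the count and flag them in a footnote. Apply this to recorded times and not to imputed ones: 9.5.3.2 would move a missing start time to randomization, which precedes the inhalation, and the event would silently drop out.
3. Confirm that the clock time of the first inhalation is in the database. The 1h and 4h post-dose spirometry mentioned in SAP 9.4 implies that sites know it, but no visible text names the field, and the exposure derivations in 15.2.1 use dates only.

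Leave the treatment-emergent definition in 15.3 unchanged, so that it stays in line with Protocol 15.2.5.2.

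The cost is a sentence or two in 15.4 and one data check. Adverse event onset times are already collected and no study procedure changes. The small downside is the need for the missing-time default, which errs towards counting the event.

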15.5 Clinical Laboratory Data

15.5.1 Hematology and Biochemistry

Clinical laboratory assessments will be performed at each visit by a certified local facility following the routine protocols at each site. As described in the clinical trial protocol (Section 13.1.5), the following clinical laboratory parameters will be reported in the eCRF:

Hematology

- White Blood Cell (WBC) count with differential,
- Red Blood Cell (RBC) count,
- Platelet count,
- Neutrophils,
- Lymphocytes,
- Monocytes,
- Eosinophils,
- Basophils,
- Neutrophils Absolute Count,
- Lymphocytes absolute counts,
- Eosinophils absolute count,
- Basophils absolute count,

- Monocyte absolute count.

Biochemistry

- Alkaline phosphatase (AP),
- Alanine aminotransferase (ALT),
- Aspartate aminotransferase (AST),
- Gamma Glutamyl Transferase (γ -GT),
- Blood urea nitrogen (BUN),
- Serum bilirubin,
- Serum creatinine,
- Sodium,
- Potassium,
- Chloride,
- Bicarbonate,
- Calcium,
- Magnesium.

Descriptive statistics of observed values and changes from baseline will be presented by visit and treatment group. The summaries described in this section will be presented relative to baseline, defined as the most recent, non-missing result on or before the date of randomization. No imputation for missing data will be performed.

All clinical laboratory data reported in the eCRF will be presented in by-patient listings.

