### 13.1.6 Vital Signs

Vital signs will be assessed at each visit.

The following vital signs will be recorded:

Systolic and diastolic blood pressure (sitting, after 5 minutes of rest), pulse rate (sitting, after 5 minutes of rest), body temperature (the same method should be used for each patient and throughout the clinical trial), and respiratory rate.

Abnormal values will be summarized by Common Toxicity Criteria (CTCAE) AE grade (version 5.0) for each patient.

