#### **15.2.5.3 Laboratory and Other Safety Evaluations**

For clinical safety laboratory test results and vital signs, the numeric values and corresponding changes from baseline will be summarized using descriptive statistics by parameter and time point. In addition to the tables showing the distribution parameters, laboratory measures will be presented in ‘shift tables’ that show the position of all patients relative to the applicable reference range at clinical trial entry, broken down by the position at clinical trial exit. Common Toxicity Criteria (CTC version 5.0) will be applied to abnormal laboratory test results and abnormal vital signs.

Parameters reflecting acute tolerability of IMP (spirometry, cough, or dyspnea) will be summarized.

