### **15.5 Sample Size Considerations**

The initial sample size was based on the following considerations. Assuming a treatment group difference for mean FEV1 change from baseline of 200 mL and a standard deviation of 350 mL at the end of treatment Week 48, an independent samples t-test with a one-sided type I error level of  $\alpha=0.025$  will have at least 80% power to reject the null hypothesis when the sample size in each treatment group is at least 50 patients. To compensate for a loss of power due to premature withdrawals, a total of 110 patients will initially be randomized.

However, due to serious enrolment problems with the present study, it was agreed with FDA to enrol approximately 220 patients with clinically defined bronchiolitis obliterans syndrome (BOS) considering the present (BOSTON-1) and the BT – L-CsA – 302 – DLT (BOSTON-2) studies combined, in order to obtain an adequately sized safety database for L-CsA inhalation. Therefore, randomization will be stopped when this target is reached and it is anticipated that much fewer than the 110 patients originally planned (i.e., approximately 50-60 patients) will be randomized in the present study.

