8 STATISTICAL CONSIDERATIONS

8.1 General Considerations and Descriptive Statistics

All report outputs will be produced using [REDACTED] version 9.2 or later, in a secure and validated environment. All tables, figures and data listings (TFLs) to be included in the report will be independently checked for consistency and integrity.

The data recorded in the eCRF will be summarized as appropriate, per treatment group and for the total group, using the following descriptive measures:

- All continuous variables will be summarized using descriptive statistics (i.e., n, mean, standard deviation (SD), median, Q1, Q3, minimum, and maximum).
- All categorical variables will be summarized by using frequency counts and percentages.
- Discrete ordinal or higher-level data will be summarized as continuous data, but a tabulation of categories may also be included, depending on the number of categories.
- For time-to-event variables, cumulative event-free survival times will be evaluated using the Kaplan-Meier method. A frequency table showing the number of events and censored patients by treatment group, will be presented along with the event-free rates (and two-sided 95% confidence). Kaplan-Meier graphs will be presented along with the number of patient-at-risk at exact time points. If different rules are not specified, patients who are free from event will be censored at the study termination.

For all measures analyzed descriptively (i.e., measures to characterize the treatment groups and their baseline status, efficacy, and safety outcomes), tabulations comparing the treatment groups will be prepared. For outcomes measured more than once, the analyses will include tabulations of the measured values by visit, as well as change from baseline. Where provided, all confidence intervals will be two-sided 95% intervals.

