15.6 Renal Function

In addition to the summarization of serum creatinine as described in previous section, renal dysfunction will be further listed and summarized by treatment group based upon the classification of AEs with the following PTs (see protocol section 13.1.5.4, Table 7 and SAP section 16):

- Blood Creatinine Increased,
- Renal Impairment,
- Renal Failure,
- Acute kidney injury,
- Azotaemia,
- Chronic kidney disease,
- Proteinuria,
- Renal disorder.

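### The visible SAP does not carry over the protocol's laboratory shift tables and CTC grading, so no planned table counts patients by arm who cross a reference limit or reach a toxicity grade

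*SAP*

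**What the plan says.** Protocol 15.2.5.3 plans three kinds of laboratory output. The first is descriptive statistics by parameter and time point. The second is a categorical display: "laboratory measures will be presented in ‘shift tables’ that show the position of all patients" against the applicable reference range at trial entry, broken down by position at trial exit. The third is grading: "Common Toxicity Criteria (CTC version 5.0) will be applied to abnormal laboratory test results and abnormal vital signs". Protocol 13.1.6 states the grading again for vital signs: "Abnormal values will be summarized by Common Toxicity Criteria (CTCAE) AE grade (version 5.0) for each patient".

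SAP 15.5.1 keeps the first: "Descriptive statistics of observed values and changes from baseline will be presented by visit and treatment group". It adds that "All clinical laboratory data reported in the eCRF will be presented in by-patient listings". SAP 8.1 defines the statistics: "All continuous variables will be summarized using descriptive statistics (i.e., n, mean, standard deviation (SD), median, Q1, Q3, minimum, and maximum". SAP 15.7 treats vital signs in the same way. Neither section visibly mentions a shift table, a toxicity grade or a reference-range category.

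For the kidney, SAP 15.6 adds an adverse-event summary: "renal dysfunction will be further listed and summarized by treatment group based upon the classification of AEs with the following PTs". Eight preferred terms follow.

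**The concern.** Renal function is a named safety endpoint in both documents, and the added drug is a calcineurin inhibitor given on top of a regimen that already includes tacrolimus. Protocol 15.5 explains the combined enrolment target across BOSTON-1 and BOSTON-2 as set "in order to obtain an adequately sized safety database for L-CsA inhalation". A report serving that aim should say how many patients in each arm had a laboratory value leave the reference range or reach a given grade. The protocol planned outputs of that kind and the visible SAP does not. Protocol section 15 makes the final SAP the analysis of record where the two differ, so these outputs are no longer planned unless they are restored.

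**Working it through.** The documents give no figure to reproduce. The check is a comparison of texts, followed by an illustration with assumed values.

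**1. Is the removal declared?** The visible part of SAP Section 16 records smaller safety changes, namely the detail on the safety set and the extra renal preferred terms. The SAP version history shows that version 3.0 updated both 15.5.1 and 15.6. No visible entry mentions shift tables or CTC grading. Several entries are redacted, so this covers visible text only.

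**2. Can the retained outputs answer how many patients per arm crossed a limit or reached a grade?**

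| Retained output | What it shows | What it leaves out |
|---|---|---|
| Mean, SD, median, quartiles by visit and arm | Location and spread | Number of patients past a limit |
| Minimum and maximum | The most extreme value at a visit | Whether one patient or several were extreme; a large relative rise from a low start |
| By-patient listings | Every value | A count or comparison by arm, unless made by hand |
| Renal preferred terms (SAP 15.6) | Patients with a reported renal event | Abnormal values not reported as events |
| Hepatic counterpart | None visible | All of the above |

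On the renal row, Protocol 13.1.1.1 makes an abnormal result an adverse event only if it points to a clinical condition that itself meets the definition. That judgement is made by investigators who know the assignment (Protocol 9.3.1). Protocol Table 7 also maps temporary and stable creatinine above 2.5 mg/dL to the same term, renal impairment, so the term alone cannot separate them.

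**3. How far would a mean move?** SAP 8.2 gives 62 randomized. With 1:1 allocation I assume 62/2 = 31 per arm. Creatinine values and SDs below are also assumed.

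One patient, baseline 1.2 mg/dL, shift in arm mean = (peak − baseline)/31:
- peak 3.0: 1.8/31 = 0.06 mg/dL
- peak 4.0: 2.8/31 = 0.09 mg/dL
- peak 5.0: 3.8/31 = 0.12 mg/dL

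95% half-width for the difference between arms in mean change = 1.96 × SD × √(2/31):
- SD 0.2: 0.10 mg/dL
- SD 0.4: 0.20 mg/dL

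A single case is therefore smaller than, or of the same order as, the noise in the comparison of means.

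Three patients, each rising from 1.5 to 3.0 mg/dL:
- shift in mean = 3 × 1.5/31 = 0.145 mg/dL
- share of the arm = 3/31 = 9.7%, so all three can lie above the upper quartile and leave median and quartiles almost unchanged
- if the rises fall at one visit and the other 28 patients do not change, SD of change = √{[3 × (1.5 − 0.145)² + 28 × 0.145²]/30} = 0.45 mg/dL, and the maximum change is 1.5 mg/dL

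The SD and maximum would signal that something happened, but not that it was three patients.

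**4. What would the protocol's own table show?** It classifies position against the reference range at entry and exit. The documents give no creatinine limit. If a local upper limit lay below 1.5 mg/dL (assumption), these three patients would be high at entry and high at exit, and no shift would appear. A rise that resolved before exit would not appear either. The 9.7% is thus what a count above 2.5 mg/dL would give, not what the entry-to-exit table would necessarily give. This is why the fix goes further than restoration.

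**The case against.** A reader might infer that the SAP reduces laboratory safety to pooled means and so hides individual toxicity. The documents do not support that. SAP 8.1 includes median, quartiles, minimum and maximum, all laboratory data are listed by patient, and SAP 15.6 widens the renal terms from the protocol's three to eight.

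A reader might also infer that this trial was kept open to build a safety database. The target of about 220 covers BOSTON-1 and BOSTON-2 together and is the point at which randomization stops. SAP 8.3 speaks of enrolment ending early.

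Other points have force:
- Protocol Table 7 gives a renal term for creatinine above 2.5 mg/dL, which narrows the investigator's discretion over coding but does not remove the judgement about reporting.
- The DMC sees creatinine and liver tests by arm during the trial. That protects patients in the trial but is not an analysis for the report.
- Changes from baseline are within patient, so a stable offset of a local laboratory largely cancels if the patient stays with it. Raw values from different laboratories are still summarized together with no visible use of their ranges.
- Parts of Section 16 and of the version history are redacted, and the table shells that SAP 9.1 mentions are not in the public documents. The tables may exist there. Protocol section 15 also does not limit the final analyses to those it describes, and requires discrepancies to be explained in the CSR.

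These points limit the finding to visible text and to a missing tabulation. They do not supply the count by arm.

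**Conclusion.** The point holds as a narrow one. Two safety outputs planned in the protocol are absent from the visible SAP, with no visible declaration. Individual abnormal values remain in the report, but no planned table counts patients by arm who cross a reference limit or reach a toxicity grade. The gap is widest for hepatic tests, which have no visible equivalent of SAP 15.6. The primary efficacy analysis is not affected. The numerical illustration rests on assumed creatinine values, SDs and 31 patients per arm. The text comparison does not depend on it, but would change if a redacted entry or the table shells contained these outputs. This is a minor matter that is cheap to improve.

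**What to change.** Restore the protocol's outputs:
- In SAP 15.5.1, reference-range shift tables by arm from entry to exit, using the range of the local laboratory that ran each sample.
- In SAP 15.5.1 and 15.7, counts of patients by CTC v5.0 grade and arm, for laboratory data and vital signs.

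Add, as extensions beyond the protocol:
- Worst post-baseline position beside exit position, so that transient abnormalities are counted.
- The number of patients by arm with creatinine above 2.5 mg/dL, and with a rise of at least 30% from baseline. Both figures already appear in Protocol 11.3.1. Here they would serve only as descriptive cut-points, with no bearing on patient management.

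If the sponsor prefers to leave the shift tables and grading out, the minimum is to list and justify the removal in SAP Section 16.

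The fix needs no new patient assessments. The cost is programming time for standard tables and the handling of local reference ranges.
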